4.3 Study Treatment Phase (start of the study intervention)

Trametinib is administered orally once daily under fasting conditions (on an empty stomach) at least 1 hour before and 2 hours after a meal. If a subject misses a dose, subject should not double the next regularly scheduled dose. However, subject can take the missed dose immediately if the next scheduled dose is at least 12 hours later. Subject should take the next dose at its usual time.

4.3.1 Dosing

Eligible subjects will be treated with trametinib administered at 0.025 mg/kg/dose (or 0.0125mg/kg/dose for critically ill subjects, infants < 10kg at enrollment, or based on clinical discretion) daily given orally by tablet or by oral solution via a nasogastric tube (NGT) or gastric tube (GT) at dose level 1 for each disease strata. Dosing will be daily on a continuous 28-day cycle, for up to 24 total cycles. Dosing will be based on weight in kilograms (kg) obtained within 7 days of starting each cycle or pre-determined dosing weight in those subjects whom fluid status fluctuates. The total daily trametinib dose should not exceed the adult dose (2mg) in any subject.

Refer to [Section 10](#) for dose modifications for toxicity.

Trametinib formulations include:

Powder for oral solution: The liquid concentration is 0.05 mg/mL. Doses of trametinib oral solution will be rounded to nearest 0.1mL (0.005 mg) for doses ≤ 0.11 mg (in oral syringes ≤ 3 mL), 0.2 mL (0.01mg) for doses > 0.11 mg (in oral syringes of 5-10 mL volume). Trametinib pediatric oral solution formulation will be administered with a graduated syringe.

Tablet formulation: Doses of tablet formulation should be rounded to the nearest 0.5mg. It is recommended that subjects drink 4 to 6 mL of water/kg body weight following dosing.

A dosing nomogram ([see Appendix II](#)) based on weight and dose level will be used to prescribe trametinib to minimize inter-subject dosing variability. If vomiting occurs after taking the oral solution formulation, the dose should not be repeated, and next dose given at its scheduled time.

4.4 Follow-up Phase

Subjects who have stopped trametinib therapy due to completion of therapy or toxicities will be followed for 30 days after treatment cessation or resolution of toxicities, whichever is longer.

4.5 Extension Phase

Subjects showing clinical benefit may continue into the extension period for up to 12 additional cycles (36 total cycles, including the treatment phase). This will be at the discretion of the treating physician and subject's family.

4.6 End of Treatment

Treatment will be discontinued if one of the below conditions are met:

- after completing up to 24 cycles of therapy (for subjects who do not participate in the extension phase); or
- after completing up to 36 cycles of therapy (for subjects who participate in the extension phase); or
- by subject (or legal guardian/LAR) decision; or
- by physician's decision if the subject has progressive disease, severe side effects or does not comply with the study requirements; or
- by decision of CaNVAS based on Safety Monitoring Board

4.7 Study Duration, Enrollment and Number of Sites

4.7.1 Duration of Study Participation

The study duration per subject may be up to 30 days of the Screening Phase, up to 24 complete cycles of Study Treatment Phase, and up to 30 days follow-up once medication has been discontinued. Subjects deriving benefit from study drug may be eligible for the 12 cycles of the Extension Phase following the initial 24 cycles of treatment.

Active recruitments will take 2 years and there will be follow up after discontinuation of study treatment for a period of 30 days.

4.7.2 Total Number of Study Sites/Total Number of Subjects Projected

The study will be a multi-site trial through the CaNVAS Consortium which currently comprises 25 sites throughout the United States.

Recruitment will stop when 39 evaluable subjects are enrolled. It is expected that approximately 45 subjects will be enrolled to produce 39 evaluable subjects.

4.8 Study Population

Study entry is open to subjects regardless of gender or ethnic background. While there will be every effort to seek out and include females and minority subjects, the subject population is expected to be no different than that of subject backgrounds at the CaNVAS consortium membership sites.

5 SUBJECT ELIGIBILITY

The study plans to enroll approximately 39 evaluable subjects in total. The study will enroll both adult and pediatric participants ≥ 2 months old

5.1 Inclusion Criteria

The eligibility criteria listed below are interpreted literally and cannot be waived. Subjects eligible for inclusion in this study must meet **all** of the following criteria:

1. Signed informed consent and assent (when applicable) from the subject, parent/guardian/LAR must be obtained prior to any study related screening procedures.
2. Males or females age ≥ 2 months to ≤ 30 years at the time of informed consent.
3. Documented laboratory validated pathogenic **or likely pathogenic** germline or somatic Ras/MAPK-pathway variant. Variants of Unknown Significance (VUS) not predicted to be pathogenic will not be allowed.
4. Subjects must have a symptomatic vascular anomaly in need of medical therapy.
5. Measurable Disease: Subjects must have at least one disease-related lesion which can be measured objectively via:
 - a. Radiographic/imaging study OR
 - b. Quantitative CBA measurement ([Appendix X](#)) If there is no quantifiable lesion by imaging, the quantitative CBA must be determined prior to enrollment and confirmed/approved by study PI and local PI.
6. Performance Level: Subjects must have a Lansky or Karnofsky performance status score of ≥ 50 (ECOG categories 0,1 or 2) within 14 days before study treatment start. Lansky scale to be used for subjects ≤ 16 years of age. Karnofsky to be used for subjects > 16 years of age. Subjects in a wheelchair, unable to walk due to condition but who are up in a wheelchair will be considered ambulatory.
7. Organ Function: Have acceptable organ function as defined as:
 - a. Renal function:
 - i. Serum creatinine concentration $\leq 1.5 \times$ institutional upper limit of normal (ULN) based on the age and sex, or creatinine clearance (CrCl) > 50 mL/min (0.84 mL/s) (as measured preferably by a nuclear glomerular filtration rate scan, timed urine collection for CrCl, or calculated by the Schwartz formula [for subjects < 18 years] or Cockcroft-Gault [for subjects ≥ 18 years] and normalized to a BSA of 1.73 m²).
 - b. Hepatic function:
 - i. Total bilirubin $\leq 1.5 \times$ upper limit of normal (ULN) for age except for subjects with confirmed Gilbert's syndrome who may only be included if the total bilirubin is $\leq 3.0 \times$ ULN or direct bilirubin $\leq 1.5 \times$ ULN
 - ii. Alanine aminotransferase (ALT) or SPGT $\leq 3 \times$ ULN
 - iii. Aspartate aminotransferase (AST) or SGOT ≤ 5 ULN

- iv. Serum albumin may be lowered in this subject population and will not be used to evaluate adequate liver function
- c. Adequate cardiac function as indicated by
 - i. Left Ventricular Shortening fraction of $\geq 27\%$ by echocardiogram **or** ejection fraction of $\geq 50\%$ by MUGA
 - ii. No documented history of congestive heart failure (New York Heart Association functional classification III-IV)
 - iii. No history of long QT syndrome, family history of idiopathic sudden death or congenital long QT syndrome
- d. Adequate Bone Marrow Function
 - i. Hemoglobin ≥ 8 g/dL (may receive RBC transfusions)
 - ii. Absolute Neutrophil Count (ANC) $\geq 750 \times 10^9/L$
 - iii. Platelets $\geq 75 \times 10^9/L$ (independent of transfusions) exception is made for Kaposiform lymphangiomatosis subjects who have a baseline coagulopathy and thrombocytopenia.
- 8. Persons who can get pregnant 11 years of age or persons with early onset menarche must have a negative serum or urine pregnancy test within 7 days prior to the initiation of the study medication.
- 9. Males and females of reproductive potential must agree to the use an acceptable method of contraception, including abstinence, a barrier method (diaphragm or condom), IM progesterone depot, intrauterine contraceptive device, or an oral contraceptive, for the duration of time when they are receiving study drug and for 3 months following last dose.
- 10. Subjects must be able to swallow tablets or liquid or use a nasogastric or gastric tube for liquid study medication administration.
- 11. Subjects who require physiologic or stress doses of steroids due to endocrine deficiencies are eligible.
- 12. Subjects who have previously received MEK inhibitors are eligible if otherwise meeting all eligibility criteria and concomitant medication requirements.

5.2 Exclusion Criteria

A potential subject must meet all of the inclusion criteria above. A potential subject who meets any of the following exclusion criteria is ineligible to participate in the study.

- 1. Patients seeking treatment for hypertrophic cardiomyopathy without a vascular anomaly
- 2. Concomitant/Prior Medications
 - a. No immunomodulating agents will be used concomitantly including mTOR inhibitors. Steroid premedication for imaging scans is allowed. Replacement therapy (eg., thyroxine, insulin, or physiologic or stress corticosteroid replacement therapy for adrenal or pituitary insufficiency, etc.) is not considered a form of systemic treatment.
 - b. Prior treatment with a MEK inhibitor or a modulator of the Ras/MAPK pathway medication as single agents or in combination are eligible for this study provided there were no known hypersensitivity or allergic reactions

- attributed to any of the components of compounds of similar composition to trametinib, no utilization within 30 days prior to enrollment, and patients have fully recovered from toxic effects of prior therapy (as determined by treating physician).
- c. mTOR inhibitors must not be given within 14 days of study drug initiation. Investigational drugs: Patients currently receiving another investigational agent are not eligible.
 - d. Investigational drugs: Patients currently receiving another investigational agent are not eligible.
 - e. Any investigational drug use within 30 days prior to enrollment. For agents that have known adverse events occurring beyond 30 days after administration, this period must be extended beyond the time during which adverse events are known to occur. The duration of this interval must be discussed with the study chair.
 - f. Cancer chemotherapy, radiotherapy, or immunomodulatory agents must not be given within 30 days of study drug initiation.
 - g. Cardiac medications: Patients currently receiving treatment for left ventricular systolic dysfunction are not eligible.
 - h. Supportive care use of anticoagulants and compression garments is allowed. Patients must have been using these interventions in an unchanged manner for 30 days before study.
3. Infection: Systemic fungal, bacterial, viral, or other infection not controlled (defined as exhibiting ongoing signs/symptoms related to the infection and without improvement, despite appropriate antibiotics or other treatment). Patients with possible fungal infections must have had at least 2 weeks of appropriate anti-fungal antibiotics and be asymptomatic.
 4. Patients with history of hepatic sinusoidal obstructive syndrome (veno-occlusive disease of the liver) in the prior 3 months.
 5. Presence of active gastrointestinal (GI) disease or other condition that will interfere significantly with absorption of drug excluding PLE.
 6. Patients with history of or current risk of retinal vein occlusion (RVO) or central serous retinopathy (CSR) or uncontrolled glaucoma or ocular hypertension.
 7. Allergic reactions: Patients with a history of allergic reaction attributed to compounds of similar chemical or biological composition to trametinib are not eligible.
 8. History of prior and or ongoing malignancy (within 5 years before informed consent except radically treated carcinoma in situ or radically treated basal-cell carcinoma of skin or thyroid gland, well-differentiated microcarcinoma or Stage 1 Wilms' tumor of a histology other than anaplastic), or ongoing investigations or treatment for malignancy at time of informed consent.
 9. Patients unable to comply with safety monitoring requirements.
 10. Patient may not be pregnant or breast feeding.
 11. Parents/guardian/LAR or subjects who, in the opinion of the Investigator, may be non-compliant with study schedules or procedures.
 12. Debulking or other major surgery performed within 30 days, at time of informed consent;

13. Clinically meaningful bleeding related to VA: Grade 2 within 14 days or Grade 3 and more within 28 days before study treatment start as per CTCAE v. 5.0.
14. Sclerotherapy/embolization for vascular complications performed within 14 days before informed consent.
15. Subjects not able to understand and to comply with study instructions and requirements (in patients, legally authorized representatives, or guardians as applicable) at time of informed consent.

Subjects that do not meet all of the enrollment criteria may not be enrolled. Any violations of these criteria must be reported in accordance with IRB Policies and Procedures.

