6 STUDY PROCEDURES

Subjects will be evaluated for study eligibility at a screening visit up to 30 days prior to enrollment on study. All laboratory tests done to confirm eligibility must be performed within 14 days unless otherwise noted prior to enrollment. Radiologic disease evaluations must be done within 30 days of enrollment. Subjects will be seen by medical providers for prior history, physical exam, and required assessments as noted below to monitor for toxicities and assess disease status. Any results falling outside of the reference ranges may be repeated at the investigator's discretion. All on-study visit procedures are allowed a window of ± 7 days unless otherwise noted. Treatment or visit delays for public holidays or weather conditions do not constitute a protocol violation but should be noted in the source documents.

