7 SUPPORTIVE CARE AND CONCOMITANT MEDICATION

7.1 Other Treatment(s)

All subjects will be allowed to receive concomitant medication and/or other non-medication treatment (e.g., rescue surgery) when clinically indicated to control comorbidities and/or complications of their VA. Rescue surgery is defined as a salvage intervention, and includes e.g. debulking surgery, orthopedic surgery, invasive vascular surgeries/procedures. As much as possible, surgery targeting VA-related lesion volume reduction should be avoided. Systemic therapy targeting Ras/MAPK pathway other than trametinib and/or any investigational/not approved medication for VA are not allowed during the conduct of the study.

During the course of the study, the subject must also not receive anti angiogenic agents for the purpose to treat VA.

The subject must discontinue from specific treatment with small molecules (such as mTOR inhibitors, AKT inhibitors) before any of study related assessments and at least 30 days before study treatment start per inclusion/exclusion criteria.

Subjects are not allowed to receive any other investigational drugs.

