7.3 Prohibited medication

No other cancer chemotherapy, radiotherapy, or immunomodulatory agents including mTOR inhibitors will be permitted while on treatment with study drug. Agents must not be given within 30 days of study drug initiation.

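### The mTOR-inhibitor washout is 14 days in exclusion 2c and the synopsis but 30 days elsewhere, and the printed ANC and synopsis platelet limits are wrong or contradictory

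*Protocol*

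**What the plan says.** **Washout.** Protocol 5.2, exclusion 2c: "mTOR inhibitors must not be given within 14 days of study drug initiation". Synopsis item 13b repeats it.

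Four other statements point to 30 days:

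- Section 7.1 names mTOR inhibitors and requires them to be stopped "before any of study related assessments and at least 30 days before study treatment start per inclusion/exclusion criteria".
- Section 7.3 puts them among immunomodulatory agents: "No other cancer chemotherapy, radiotherapy, or immunomodulatory agents including mTOR inhibitors will be permitted while on treatment with study drug". It continues: "Agents must not be given within 30 days of study drug initiation".
- Exclusion 2a makes the same grouping: "No immunomodulating agents will be used concomitantly including mTOR inhibitors".
- Exclusion 2f sets the interval for that group: "Cancer chemotherapy, radiotherapy, or immunomodulatory agents must not be given within 30 days of study drug initiation". The synopsis carries the same grouping at the start of item 13 and the same interval as item 13e.

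The lead-in to 5.2 makes each exclusion sufficient by itself: "A potential subject who meets any of the following exclusion criteria is ineligible to participate in the study".

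**Baseline imaging.** Section 6: "Radiologic disease evaluations must be done within 30 days of enrollment". Section 6.1 gives 4 weeks.

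**Blood counts.** Inclusion 7d in 5.1 and the matching synopsis item both print the ANC limit as 750 × 10^9/L. The platelet limit is 75 × 10^9/L in 5.1 and 1000 × 10^9/L in the synopsis, each with an exception for Kaposiform lymphangiomatosis. Section 5.1 says that its criteria are applied to the letter, with no waivers. Appendix IX requires ANC above 1,000 and platelets above 75,000 to begin a cycle and states no exception.

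**The concern.** Section 7.1 refers the reader to the eligibility criteria for its 30-day figure, but the one criterion there that sets an mTOR-specific washout says 14 days. A subject 20 days off sirolimus satisfies 2c and breaches 7.1, 7.3 and 2f. Two sites could decide that case differently, and one of them would have a reportable eligibility violation. The case is plausible in this population, because section 1.1 describes sirolimus as useful in some subjects with severe disease.

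The secondary risk is to the baseline. The screening scan is the reference for radiologic change at the end of cycle 6, which is one component of the primary response. If a site worked from the 14-day line alone, that scan could be taken while the subject was still on an mTOR inhibitor.

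The count limits matter for a simpler reason: they are operative, non-waivable thresholds. As printed, the ANC limit is on the wrong scale in both places, and the platelet limit depends on which list is read.

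**Working it through.** There is no sample-size or power figure to reproduce. The check is a comparison of text, some window arithmetic and a unit conversion.

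**1. Do the washout rules agree?**

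- 14 days: 2c and synopsis 13b.
- 30 days with mTOR inhibitors named: 7.1 and 7.3.
- 30 days by classification: 2a with 2f, and the same pair in the synopsis.

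Because any single exclusion is enough, 2f makes a subject 14 to 30 days off drug ineligible and leaves 2c with no effect. The alternative is that 2c is a deliberate exception to 2f, but no section says so, and 7.1 and 7.3 say the opposite. The rules therefore conflict within each list and between sections.

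**2. How much of the imaging window could fall on drug under the 14-day line alone?**

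Let W be the imaging window before enrollment (30 days in section 6, 28 days in 6.1) and k the days from enrollment to first dose (0 to 14). The last mTOR dose that 2c allows is 14 − k days before enrollment. On-drug part of the window = W − (14 − k).

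- k = 0, W = 30: 30 − 14 = 16 days.
- k = 0, W = 28: 28 − 14 = 14 days.
- General k: 16 + k and 14 + k days.

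So 14 and 16 are the values for treatment starting at enrollment, and they are not upper bounds. Section 4.2 sets separate time limits for enrollment and for start of therapy, so k need not be 0.

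Under a 30-day washout the same formula gives W − (30 − k), or zero where that is negative. At k = 0 both windows give 0 days. At k above 0 the 30-day window gives k days. A 30-day washout alone therefore does not guarantee an off-drug scan. The separate rule in 7.1, that the drug stops before study assessments, does that work.

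**3. ANC** (1 × 10^9/L = 1,000 per microlitre)

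- Printed: 750 × 10^9/L = 750,000 per microlitre.
- Apparent intent: 750 per microlitre = 0.75 × 10^9/L.
- Ratio: 750,000 / 750 = 1000.

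The intent is inferred from the number itself and from the other ANC values in the protocol: 500 per microlitre in 10.2.2 and 1,000 in Appendix IX. No section states it.

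**4. Platelets**

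- Synopsis: 1000 × 10^9/L = 1,000,000 per microlitre.
- Section 5.1: 75 × 10^9/L = 75,000 per microlitre, the same figure as in Appendix IX.
- Ratio: 1000 / 75 = 13.3.

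**5. Kaposiform lymphangiomatosis exception**

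Section 5.1 and the synopsis exempt these subjects from the platelet limit. Appendix IX applies 75,000 without the exemption, so a subject admitted under it could be held at the start of a cycle.

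**The case against.** The best reply is that the protocol, read whole, already resolves to the stricter rule. Section 7.1 forbids on-drug baseline assessments, 2f imposes 30 days, and the synopsis carries the same counter-rule as item 13e, so even a synopsis-only reader meets the conflict. Only someone who reads one line is misled. That stands, and it limits the consequence. It does not remove the conflict, because the 14-day line is the only mTOR-specific washout in the eligibility list and 7.1 sends the reader to that list. Section 4.2 also lets clinically indicated studies done before consent serve as screening values, so a site could argue that such a scan is not a study-related assessment under 7.1.

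On ANC, the reply is that nobody could meet 750,000 per microlitre, so sites will correct it in their heads. That is probably true in practice, but a criterion that cannot be waived should not depend on guesswork. On platelets, the synopsis figure may be a text-extraction fault. This cannot be excluded, and 5.1 has the sensible value.

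Four stronger readings are tempting, and the documents do not support them:

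- A reader might infer that the plan permits an on-drug baseline or biases the primary endpoint. Section 7.1 prohibits it, and neither the direction of any bias nor the number of subjects coming off mTOR inhibitors is given.
- A reader might want an exposure figure for the patient-reported and clinical-benefit baselines. Sections 8.2.2 and 8.2.3 place these at enrollment, the design schema places them at screening, and the gap to first dose is open, so no figure can be defended.
- A reader might see the Appendix IX ANC of 1,000 as contradicting eligibility at 750. Counts for starting a cycle may differ from eligibility counts, the schema refers to separate criteria for subsequent cycles, and Appendix IX does not say that it governs cycle 1.
- A reader might take the 14 days as a debatable design choice. Nothing presents it as one. It is an internal inconsistency.

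**Conclusion.** The point holds as an internal inconsistency in the eligibility rules. The washout differs by 16 days (30 − 14) between 2c with synopsis 13b and everything else that bears on mTOR inhibitors, and sites can reach opposite eligibility decisions for a subject 14 to 30 days off drug. An on-drug screening scan is possible only for a reader of the 14-day line alone. The 14 to 16 days quoted for it assume treatment starts at enrollment, with more exposure possible if it starts later. No effect on the response rate is shown.

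The ANC error is 1000-fold and identical in both lists, which makes an extraction fault unlikely. The intended 750 per microlitre is an inference for the sponsor to confirm. The platelet contradiction is 13-fold as printed, with the extraction caveat. The missing Kaposiform lymphangiomatosis exception is the only part of Appendix IX that needs attention.

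**What to change.** - State one washout in 2c, 2f, 7.1, 7.3 and synopsis items 13b and 13e. Either use 30 days throughout, or keep 14 days as an explicit exception for mTOR inhibitors, written into each of those places.
- Under either option keep the 7.1 rule that baseline assessments follow discontinuation, and refer to it in section 6 beside the imaging window.
- Correct ANC to 0.75 × 10^9/L (750 per microlitre, sponsor to confirm) in 5.1 and the synopsis.
- Make the synopsis platelet limit 75 × 10^9/L.
- Add the Kaposiform lymphangiomatosis platelet exception to the Appendix IX cycle-start counts.

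The cost is amendment wording and a memo to sites. Choosing 30 days keeps some subjects off systemic therapy for up to 16 days longer than 2c would, which is a real burden in severe disease. The 14-day exception avoids it, provided the scan is still taken off drug.
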